**Control group:**

- Let  $C_{\text{antibiotic}ij}$  be the cost of antibiotic therapy for patient  $i$  using antibiotic  $j$  in the intervention group.
- Total cost for antibiotic therapy for the control group  $C_{\text{antibiotic, control}}$  is:

$$C_{\text{antibiotic, control}} = \sum_{i=1}^{266} \sum_{j=1}^n C_{\text{antibiotic}ij}$$

- Per patient cost for antibiotic therapy in the control group  $\bar{C}_{\text{antibiotic, control}}$  is

$$\bar{C}_{\text{antibiotic, control}} = \frac{C_{\text{antibiotic, control}}}{266}$$

**Hospital Stay Costs**

- Let  $LOS_i$  be the length of stay for patient  $i$ .
- Let  $C_{\text{inpatient\_day}}$  be the average inpatient cost per day for septic patients. The analysis will use an estimated cost from previous research.

**Intervention Group:**

- Total hospital stay cost for the intervention group  $C_{\text{hospital, intervention}}$  is

$$C_{\text{hospital, intervention}} = \sum_{i=1}^{266} LOS_i \times C_{\text{inpatient\_day}}$$

- Per patient hospital stay cost in the intervention group  $\bar{C}_{\text{hospitl, intervention}}$  is

$$\bar{C}_{\text{hospital, intervention}} = \frac{C_{\text{hospital, intervention}}}{266}$$

**Control Group:**

- Total hospital stay cost for the control group  $C_{\text{hospital, control}}$  is

$$C_{\text{hospital, control}} = \sum_{i=1}^{266} LOS_i \times C_{\text{inpatient\_day}}$$

---

**STATISTICAL ANALYSIS PLAN**

---

- Per patient hospital stay cost in the control group  $\bar{C}_{\text{hospital, control}}$  is

$$\bar{C}_{\text{hospital, control}} = \frac{C_{\text{hospital, control}}}{266}$$

**3.7.2 Cost Comparison**
**Total costs**
**Intervention Group:**

- Total per patient cost in the intervention group  $\bar{C}_{\text{total, intervention}}$  is:

$$\bar{C}_{\text{total, intervention}} = \bar{C}_{\text{antibiotic plus PCT, intervention}} + \bar{C}_{\text{hospital, intervention}}$$

**Control Group:**

- Total per patient cost in the intervention group  $\bar{C}_{\text{total, control}}$  is:

$$\bar{C}_{\text{total, control}} = \bar{C}_{\text{antibiotic, control}} + \bar{C}_{\text{hospital, control}}$$

**3.7.3 Costs Analysis**

- Difference in average total cost per patient  $\Delta \bar{C}_{\text{total}}$  is:

$$\Delta \bar{C}_{\text{total}} = \bar{C}_{\text{total, control}} - \bar{C}_{\text{total, intervention}}$$

- Perform t-test to determine if  $\Delta \bar{C}_{\text{total}}$  is statistically significant.

**3.7.4 Cost Savings**

- Calculate absolute cost savings per patient  $Savings_{\text{absolute}}$ :

$$Savings_{\text{absolute}} = \Delta \bar{C}_{\text{total}}$$

- Calculate percentage cost savings  $Savings_{\text{percentage}}$ :

$$Savings_{\text{percentage}} = \left( \frac{\Delta \bar{C}_{\text{total}}}{\bar{C}_{\text{total, control}}} \right) \times 100$$

---

**STATISTICAL ANALYSIS PLAN**

---

**4. Appendix**

In the systematic review titled, "Metrics for quantifying antibiotic use in the hospital setting: results from a systematic review and international multidisciplinary consensus procedure," the panel recommended that antibiotic use should be expressed using at least two metrics simultaneously (1). For our analysis of antibiotic use, we will apply three metrics: Length of Therapy (LOT), Days of Therapy (DOT), and Defined Daily Dose (DDD)

**4.1 Guide to the calculation of the Length of Therapy (LOT), Days of Therapy (DOT) and the Defined Daily Dose (DDD)**
**Length of therapy (LOT) calculation.**

LOT is defined as the number of days of antibiotic treatment during the study period. Length of treatment will be measured from the day of enrolment to completion of the study follow up (28 days after hospital discharge). The primary outcome data for participants with recurrent infections will be censored at the time of recurrent infection diagnosis, i.e. the recurrent date will be used as the stop date in the calculation of LOT. If the recurrent infection occurs after the patient already stopped antibiotics for the initial presenting infection, the actual stop date of the last dose of antibiotics administered for the initial infection will be used in the LOT calculations and not the recurrent infection date.

The stop date for each antibiotic will be when the treating team discontinues it. In special circumstances, such as patients who left the hospital against medical advice or were transferred to another facility, the stop date will be recorded as the date they left or were transferred, as it was not feasible for the study team to track antibiotic data consistently in both arms beyond these points. If a patient developed an alternative diagnosis during the study that required an extended or modified antibiotic regimen, each case was reviewed individually by an investigator panel to determine the maximum antibiotic duration that could be included in the analysis.

**Scenario 1:** As an example, suppose patient A was admitted to the hospital on 02 February 24 at 10:00 AM due to a urinary tract infection. At 4:00 PM the same day, this patient was enrolled into the PROCALBAN study and was discharged from the hospital on 08 February 24 at 10:00 AM. This patient received intravenous ceftriaxone, 1 gram administered every 12 hourly from the date of enrolment and then upon discharge, this patient was prescribed oral cefuroxime, 500mg every 8 hours, for a duration of 7 days i.e. the actual stop date time for this oral cefuroxime will be subsequently recorded in the database by the end of follow-up for this patient. The calculation of LOT (the primary outcome) will proceed as follows:

1. Hospital stay duration during enrolment will be calculated as follows:
  - Enrollment: February 2nd, 4:00 PM
  - Discharge: February 8th, 10:00 AM
  - Hospital stay duration:
    - February 2nd, 4:00 PM to February 3rd, 4:00 PM = 24 hours
    - February 3rd, 4:00 PM to February 4th, 4:00 PM = 24 hours
    - February 4th, 4:00 PM to February 5th, 4:00 PM = 24 hours
    - February 5th, 4:00 PM to February 6th, 4:00 PM = 24 hours
    - February 6th, 4:00 PM to February 7th, 4:00 PM = 24 hours
    - February 7th, 4:00 PM to February 8th, 10:00 AM = 18 hours

## STATISTICAL ANALYSIS PLAN

- Total hospital stay duration =  $24 + 24 + 24 + 24 + 24 + 18 = 138$  hours (approximately 5 days and 18 hours).

Definition of 'hospital stay duration':

Hospital stay duration = discharge date time – enrolment date time.

If only date (without time) is available for one or both date fields used in these calculations, the dates will be used for calculating the length of therapy.

2. Post-discharge oral antibiotic therapy duration:

- Prescribed for 7 days
- Total duration for oral cefuroxime therapy:  $7 \text{ days} * 24 \text{ hours/day} = 168 \text{ hours}$

3. Total duration up to discharge:

- Total therapy duration = Hospital stay duration + oral cefuroxime therapy duration
- Total therapy duration = 138 hours (hospital stay) + 168 hours (oral cefuroxime therapy) = 306 hours (approximately 12 days and 18 hours)

In total, the total length of therapy from enrolment up to discharge for Patient A is approximately 12 days and 18 hours, or 306 hours. For analysis, this will be expressed in days.

In short **LOT**=stop date time (for last dose) – start date time (for first dose).

Similarly, if only date (without time) is available for one or both date fields used in these calculations, the dates will be used for calculating the length of therapy.

**Scenario 2** : A patient is prescribed ceftriaxone IV and oral clarithromycin to treat an infection. Both antibiotics are started on 03 September 2024 and discontinued on 07 September 2024.

- **LOT Calculation:** Since LOT is based on the total duration of exposure to any antibiotic, regardless of how many different antibiotics are administered, we calculate it by counting the calendar days from the start date to the stop date.
  - **Start Date:** 03 September 2024
  - **Stop Date:** 07 September 2024
  - **Total LOT:** 5 calendar days

**Result:** The LOT for this course of therapy is **5 days**, representing the patient's exposure to antibiotic treatment over this period, irrespective of the number of antibiotics given.

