#### 2.1.2 Primary endpoint

**Length of antibiotic treatment:** number of days of antibiotic treatment during the study period (till 28 days after hospital discharge). The primary outcome data for participants with recurrent infections will be censored at the time of recurrent infection diagnosis.

---

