### Definition of DOT (Days of therapy)

One DOT represents the administration of a single antibiotic on a given day regardless of the number of doses administered or dosage strength. If a patient receives more than one antibiotic, the DOTs for all the given antibiotic therapies will be added together to come up with the total DOT for this patient. DOT will be greater than or equal to LOT because each antibiotic administered counts as a separate DOT.

For calculating DOT, the start time for any antibiotic initiated prior to enrolment will be recorded as the time of enrolment, while for antibiotics started post-enrolment, the actual start time will be used.

**Scenario:** As an example, suppose patient B was admitted to the hospital on May 5, 2024 with pneumonia and was discharged on May, 9, 2024. During the hospital stay, Patient B received Intravenous

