## STATISTICAL ANALYSIS PLAN

ceftriaxone every 12 hours, denoted by "1 dot" for each day. Upon discharge, Patient B was prescribed oral amoxicillin 500mg every 8 hours to be taken at home for 7 days, denoted by "1 DOT " for each day.

Calculation:

1. Hospital stay duration: 4 days
2. Intravenous ceftriaxone therapy: Given every 12 hours for 4 days (total of 2 doses per day, counted as "1 DOT " for each day)
3. Oral amoxicillin therapy: Prescribed for 7 days, taken every 8 hours (total of 3 doses per day, counted as "1 DOT " for each day)
4. Overall Therapy Duration: 4 days (hospital stay) + 7 days (oral antibiotic therapy) = 11 DOTs

The actual DOT for each antibiotic drug that was given will be recorded by the end of the patient's follow-up and will be used for the calculations. The actual date (or date time if available) will be used to calculate the DOT for each antibiotic drug and then these DOTs will be summed up.

In calculating DOT, if an antibiotic is administered every 48 hours, it will not be counted as every alternate day. For example, if a patient receives meropenem every 48 hours over a span of 7 days, it will be counted as 7 DOT, not 4 DOT. This approach considers the overall exposure to the antibiotic.

**Number of days of parenteral antibiotic during hospitalisation period:** will be measured from the day of enrolment to the day of stopping of parenteral antibiotic during hospitalisation period

**Number of days of antibiotic treatment during the hospitalisation period:** Length of treatment will be measured from the days of enrolment to stopping of antibiotic during hospitalisation period.

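### The SAP's derivation of length of therapy, the primary outcome, is inconsistent on how days are counted, on gaps between courses, and on the stop date when antibiotics continue after an alternative diagnosis

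*SAP*

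**What the plan says.** **Definition.** SAP section 2.1.2 makes the primary endpoint the "number of days of antibiotic treatment during the study period (till 28 days after hospital discharge", with censoring at a recurrent infection. Section 4.1 repeats it: "LOT is defined as the number of days of antibiotic treatment during the study period".

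**Formula.** After Scenario 1, section 4.1 condenses LOT to a subtraction. Its first term is "stop date time (for last dose", and the date-time of the first dose is taken from it. Scenario 1 (Patient A) is worked in hours.

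**Fallback.** Where a clock time is missing from either field, "the dates will be used for calculating the length of therapy".

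**Scenario 2.** For a patient with dates only, "we calculate it by counting the calendar days from the start date to the stop date". The result given for 3 to 7 September is 5 days.

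**Days of therapy (DOT).** "The actual date (or date time if available) will be used to calculate the DOT for each antibiotic drug". The Patient B example takes 5 to 9 May as 4 days and arrives at 11 DOT. The section also asserts that "DOT will be greater than or equal to LOT because each antibiotic administered counts as a separate DOT". For a drug given every 48 hours over 7 days, "it will be counted as 7 DOT, not 4 DOT".

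**Restarts.** Section 3.3 B keeps patients who resume antibiotics without a recurrent infection in both ITT and per protocol. It makes an exception for antibiotics begun after discharge for reasons other than recurrence.

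**Alternative diagnosis, antibiotics continued.** Section 4.2 (Atypical Cases), item 2, takes the date of that diagnosis as the stop date for the initial treatment. Section 4.1 has an investigator panel set the maximum includable duration case by case when the regimen is extended or modified. The timepoints table in the other section numbered 4.2 leaves atypical cases to team discussion.

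**The concern.** LOT is the primary endpoint, so its derivation should give one value per patient whoever programs it. Here two competent programmers could both follow the SAP and differ on three kinds of record: those without clock times, those with a stop and restart, and those where antibiotics run on after an alternative diagnosis.

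The LOT means and medians by arm in Table 2 depend on which reading is used. The treatment contrast is at risk only if the affected records are unequally distributed between arms. That cannot be ruled out from this document: the trial is not blinded, the intervention acts on stopping, and the SAP does not say that discretionary stop dates are decided without knowledge of arm.

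**Working it through.** **1. Counting convention**

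Inputs: dates and times in the Scenario 1, Scenario 2 and Patient B examples of section 4.1.

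- Scenario 1 reproduces with the formula. 2 Feb 16:00 to 8 Feb 10:00 is 5 × 24 + 18 = 138 h. Adding 7 × 24 = 168 h gives 306 h, and 306 / 24 = 12.75 days.
- Scenario 2 does not. 7 − 3 = 4 days, against the stated 5. Only stop − start + 1 gives 5, and no formula states that.
- Patient B goes the other way. 9 − 5 = 4 days, and 4 + 7 = 11 DOT. The inclusive count used in Scenario 2 would give 5, and 5 + 7 = 12.

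Size of the difference, using Patient A's in-hospital part:

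| Convention | Days |
|---|---|
| Hours (138 / 24) | 5.75 |
| Date subtraction (8 − 2) | 6 |
| Inclusive dates (8 − 2 + 1) | 7 |

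With clock times, 3 to 7 September could be anything from just over 3 to just under 5 elapsed days. The inclusive count of 5 therefore exceeds elapsed time by 0 to 2 days. The average excess is 1 day if start and stop times of day have the same mean.

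If Scenario 2 illustrates the fallback, timed and date-only records sit on scales about 1 day apart. If it does not, the count for date-only records is unstated.

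**2. Gaps between courses**

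Take one drug on days 1–3 and again on days 8–10, with no recurrence.

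- Days with treatment: 3 + 3 = 6. DOT, one per day of administration: 6.
- First-to-last span: 10 − 1 = 9 by subtraction, or 10 inclusively.

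The span exceeds both the number of treatment days and the DOT, so it conflicts with the endpoint definition and with the statement that DOT is never below LOT.

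**3. Stop date when antibiotics continue after an alternative diagnosis**

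| Place in SAP | Stop date for analysis |
|---|---|
| 4.2 Atypical Cases, item 2 | Date of the alternative diagnosis |
| 4.1, extended or modified regimen | Maximum duration set by a panel |
| 4.2 timepoints table, atypical cases | Set by team discussion |

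Melioidosis, the example in item 2, is described there as needing a prolonged course. It therefore fits both item 2 and the panel rule. Nothing says which prevails. Item 5 does produce a duration, through a third investigator, but only when investigators disagree about the final diagnosis.

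**4. Effect on the comparison**

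Take the planning means of section 2.3 and add 1 day to everyone: 5.2 + 1 = 6.2 and 3.2 + 1 = 4.2, and the difference is still 2.

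A shift in the difference needs unequal shares. The SAP gives none, so these are assumptions only:

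- Date-only share differing by 0 to 20 percentage points, 1 day each: 0 to 0.20 × 1 = 0 to 0.2 day.
- Restart share differing by 5 points, 4-day gap: 0.05 × 4 = 0.2 day.
- Restarts in one arm only, 5% to 20%, mean gap 5 days: 0.05 × 5 = 0.25 to 0.20 × 5 = 1.0 day.

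The answers run from nothing to half the planned 2-day effect, depending wholly on the inputs chosen.

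**The case against.** **Counting.** It can be said that Scenario 2 simply shows the date-only fallback. The SAP does not say so, and if it were so the two scales would be mixed within one variable. It can also be said that the formula, Scenario 1 and Patient B all use elapsed time or subtraction, so that Scenario 2 is the outlier and the only thing to correct. That is a fair choice of remedy, but the contradiction remains until it is made.

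**Gaps.** A reader might infer that the SAP prescribes counting antibiotic-free days. It does not. The formula is a shorthand that follows a continuous course, and Patient A's total was built by adding components. The endpoint definition, and Scenario 2's reference to exposure, point towards leaving gaps out. What stands is that the formula is worded generally, gives the wrong answer for a restart if applied as written, and is not corrected by any gap rule. The group affected is probably small, mainly restarts before discharge.

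**Stop dates.** A reader might infer that all the atypical-case rules contradict one another. Most cover different situations: item 1 can be read as therapy not continued, item 3 as an additional diagnosis, item 4 as conditions mimicking sepsis, and section 3.3 A.a agrees with item 4. The panel can also be read as the body that applies these rules. What stands is narrower: the fixed date in item 2 against the discretion in section 4.1 and the timepoints table.

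**Populations.** Nor can one say that the stop-date problem touches ITT alone. Sections 1.1 and 3.3 A.a remove patients who meet exclusion criteria or have a non-infectious alternative diagnosis from per protocol. Melioidosis is an infection, and whether it meets an exclusion criterion cannot be settled from the SAP text at hand.

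**Conclusion.** The concern holds in three limited parts. The counting contradiction is certain: 4 days by the formula against 5 as stated, with the Patient B example on the opposite side from Scenario 2. Timed and date-only records can differ by about 1 day on average, assuming start and stop times of day have the same mean. The gap problem follows from a literal reading of the summary formula. The stop-date conflict is confined to antibiotics continued after an alternative diagnosis.

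A constant offset leaves the mean difference unchanged and moves the arm means and medians in Table 2. Bias arises only if completeness of clock times, restarts or discretionary dates differ by arm. Neither a reassuring ceiling nor an alarming figure for that bias is supported: every value in the illustration above rests on assumed shares and gaps. The sample size calculation is not affected.

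This should be fixed, because it concerns the primary endpoint and the remedy is cheap.

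**What to change.** 1. **One counting convention.** State it for all patients, for both LOT and DOT, and for date-only records, and correct the examples that do not match. Either convention works:
   - *Elapsed time or date subtraction.* Scenario 2 becomes 4. Say how a course that starts and stops on the same date counts, since subtraction gives 0.
   - *Calendar days on an antibiotic.* Scenario 1 and its formula change, and so does Patient B's DOT of 11. Within-day precision is lost where times were recorded; elapsed time could be kept as a sensitivity analysis for those records.
2. **Gaps.** Replace the first-to-last formula with a sum over treatment periods that leaves out days between courses. Carry the existing 48-hour counting rule over to LOT, so that a dosing interval is not taken for a gap. If LOT is the time covered by at least one drug and DOT is the sum over drugs on the same convention, DOT cannot fall below LOT.
3. **Stop dates, for the analysis dataset only.** Reconcile section 3.3 A.a, section 4.1, the timepoints table and the atypical-case items into one derivation with an order of precedence. Limit panel discretion to cases that the rule does not settle, preferably decided without knowledge of arm.

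**Cost.** SAP wording and a re-derivation from dates already recorded. Section 4.1 describes the panel review in the past tense, so decisions already made need checking against the reconciled rule.

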### Definition of DOT (Days of therapy)

One DOT represents the administration of a single antibiotic on a given day regardless of the number of doses administered or dosage strength. If a patient receives more than one antibiotic, the DOTs for all the given antibiotic therapies will be added together to come up with the total DOT for this patient. DOT will be greater than or equal to LOT because each antibiotic administered counts as a separate DOT.

For calculating DOT, the start time for any antibiotic initiated prior to enrolment will be recorded as the time of enrolment, while for antibiotics started post-enrolment, the actual start time will be used.

**Scenario:** As an example, suppose patient B was admitted to the hospital on May 5, 2024 with pneumonia and was discharged on May, 9, 2024. During the hospital stay, Patient B received Intravenous

## STATISTICAL ANALYSIS PLAN

ceftriaxone every 12 hours, denoted by "1 dot" for each day. Upon discharge, Patient B was prescribed oral amoxicillin 500mg every 8 hours to be taken at home for 7 days, denoted by "1 DOT " for each day.

Calculation:

1. Hospital stay duration: 4 days
2. Intravenous ceftriaxone therapy: Given every 12 hours for 4 days (total of 2 doses per day, counted as "1 DOT " for each day)
3. Oral amoxicillin therapy: Prescribed for 7 days, taken every 8 hours (total of 3 doses per day, counted as "1 DOT " for each day)
4. Overall Therapy Duration: 4 days (hospital stay) + 7 days (oral antibiotic therapy) = 11 DOTs

The actual DOT for each antibiotic drug that was given will be recorded by the end of the patient's follow-up and will be used for the calculations. The actual date (or date time if available) will be used to calculate the DOT for each antibiotic drug and then these DOTs will be summed up.

In calculating DOT, if an antibiotic is administered every 48 hours, it will not be counted as every alternate day. For example, if a patient receives meropenem every 48 hours over a span of 7 days, it will be counted as 7 DOT, not 4 DOT. This approach considers the overall exposure to the antibiotic.

**Number of days of parenteral antibiotic during hospitalisation period:** will be measured from the day of enrolment to the day of stopping of parenteral antibiotic during hospitalisation period

**Number of days of antibiotic treatment during the hospitalisation period:** Length of treatment will be measured from the days of enrolment to stopping of antibiotic during hospitalisation period.

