### 2.1.3 Secondary objectives and endpoints

- To assess if procalcitonin guided de-escalation reduces antibiotic **consumption** and days of therapy with antibiotics.

- Consumption of antibiotics expressed as the Defined Daily Dosage (DDD)

*Definition of DDD: The basic definition for a defined daily dose is the assumed average maintenance dose per day for a drug used in its main indication in adults. Antibiotic use using the WHO DDD definition ([https://www.whocc.no/atc\\_ddd\\_index/](https://www.whocc.no/atc_ddd_index/)) will be determined for the most frequently prescribed Drugs in Bangladesh*

- Days of therapy with antibiotics (DOT)

Definition of DOT: One DOT represents the administration of a single antibiotic on a given day regardless of the number of doses administered or dosage strength. If a patient receives more than one antibiotic it will be added on with DOT of the first antibiotic. (Dalton et al. 2015)

- Number of days of parenteral antibiotic during hospitalisation period
- Number of days of antibiotic treatment during the hospitalisation period.

- To assess the safety of procalcitonin guided de-escalation of treatment
  - Overall mortality, mortality-associated with recurrent infection, and non-lethal recurrent infections.
- To assess the effect of procalcitonin guided de-escalation on length of hospital stay
  - Duration of hospital stay (ICU/ general ward)
- To determine the spectrum of antimicrobial resistance among bacteria identified in clinical specimens from Bangladeshi patients hospitalized with sepsis
  - Bacterial isolates from blood cultures will be identified, tested for antibiotic susceptibility. In a subset of antibiotic resistant isolates, genetic correlates of resistance will be assessed (A comprehensive microbiological analysis plan is provided in section 3.6).
- To compare the patient care costs between study arms
  - Direct medical costs of prescribed antibiotics, the PCT assay and hospital stay costs.

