### DDD (Defined Daily Dose)

According to WHO "The DDD is the assumed average maintenance dose per day for a drug used for its main indication in adult"

In the absence of electronic medication management systems, the Defined Daily Dose (DDD) is a valuable metric for assessing drug consumption. The Anatomical Therapeutic Chemical (ATC)/DDD methodology, endorsed by the World Health Organization (WHO), is an internationally recognised standard for evaluating drug usage. Guidelines for calculating DDD can be found on the WHO website [here](#). In this study, we will apply the WHO ATC/DDD methodology to determine DDD, with the aim of producing high-quality, practical, and comparable drug utilisation statistics (2).

Drug utilisation data expressed in DDDs offers an approximate estimate of consumption but does not precisely reflect actual usage. DDDs serve as a standardised unit of measurement, unaffected by factors such as price, currency, packaging size, or strength, allowing researchers to examine trends in drug utilisation and compare usage across different population groups.

To calculate the Defined Daily Dose (DDD) for each antibiotic, use the following steps:

1. **Identify the Route of Administration:** Confirm the administration route (e.g., IV, oral) for each antibiotic dose, as the DDD value varies with the route.
2. **Total Dose Administered:** Sum the total dose of each antibiotic administered per patient, as recorded in the dataset.

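### The parenteral-antibiotic-days endpoint is calculated as a span from enrolment, which over-counts late-starting courses and does not settle interrupted or zero-parenteral courses

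*SAP*

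**What the plan says.** SAP 2.1.3 names the secondary endpoint "Number of days of parenteral antibiotic during hospitalisation period". Appendix 4.1, at the end of the DOT material, gives its calculation: it "will be measured from the day of enrolment to the day of stopping of parenteral antibiotic during hospitalisation period". The companion endpoint, antibiotic days in hospital, follows the same pattern: "Length of treatment will be measured from the days of enrolment to stopping of antibiotic during hospitalisation period".

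Three nearby provisions matter.

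- The start rule is written for DOT: "For calculating DOT, the start time for any antibiotic initiated prior to enrolment will be recorded as the time of enrolment". Under the same rule, a drug begun later takes its true start.
- For DOT, dates are taken drug by drug: "The actual date (or date time if available) will be used to calculate the DOT for each antibiotic drug".
- For DDD, step 1 reads "Confirm the administration route (e.g., IV, oral) for each antibiotic dose, as the DDD value varies with the route".

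The timepoint table in section 4.2 has columns for LOT, DOT and DDD only.

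**The concern.** The name of the endpoint and its calculation describe different quantities. A count of parenteral days and the time from enrolment to the parenteral stop agree when parenteral treatment begins at enrolment and runs without a break until it stops. The clock here starts at enrolment, not at the first parenteral dose, and nothing removes days without a parenteral drug.

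The SAP foresees courses that break the pattern. Section 3.3 keeps patients who restart antibiotics without a recurrent infection in both the ITT and PP analyses, apart from certain restarts after discharge. The introduction (section 2) counts prolonged use of intravenous lines among the consequences of long antibiotic therapy that the strategy may reduce. Of the listed secondary endpoints, this is the only one restricted to parenteral treatment. The trial is unblinded, so the choice of stop and the value for a patient with no parenteral treatment should not be left until the data are in view.

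**Working it through.** The SAP gives no worked figure for this endpoint, so there is none to reproduce. I applied its rule to constructed courses and compared the result with a direct count.

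**Convention.** Enrolment is day 1 and both end days count, as in Scenario 2 of Appendix 4.1, where 3 to 7 September gives 7 − 3 + 1 = 5 days.

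**Formulas.**
- Span under the SAP rule: S = stop day − enrolment day + 1.
- Count named by the endpoint: C = number of days with a parenteral drug.

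The SAP refers to the day of stopping without saying which stop applies when there are several, so both readings are shown.

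| Course in hospital | C | S, first stop | S, last stop |
|---|---|---|---|
| IV d1–5 | 5 | 5 | 5 |
| IV d1–3, oral d4–7 | 3 | 3 | 3 |
| Oral d1–3, IV d4–6 | 3 | 6 | 6 |
| None d1–2, IV d3–5 | 3 | 5 | 5 |
| IV d1–2, oral d3–5, IV d6–7 | 4 | 2 | 7 |
| IV d1–2, none d3–5, IV d6–7 | 4 | 2 | 7 |
| Oral d1–5 | 0 | undefined | undefined |

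**Late start.** For oral d1–3 then IV d4–6, S = 6 − 1 + 1 = 6 and C = 6 − 4 + 1 = 3. The excess of 3 is the three oral-only days. There is only one stop, so the choice of stop makes no difference.

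**Interrupted course.** C = 2 + 2 = 4. The last stop gives 7 − 1 + 1 = 7, an excess of 3. The first stop gives 2 − 1 + 1 = 2, a deficit of 2. Neither reading returns the count.

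**Plain subtraction.** If the span is taken as stop day minus enrolment day, every S falls by 1. IV d1–3 then scores 2 and oral d1–3 then IV d4–6 scores 5. Two courses with the same three parenteral days still differ by 3.

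**Companion endpoint (any antibiotic in hospital).** IV d1–2, none d3–5, IV d6–7 scores 7 on the last stop or 2 on the first, against 4 days on treatment. If oral treatment fills the gap, the span of 7 is correct.

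**Repair elsewhere in the SAP.** The actual-start rule would correct the late-start case, but it is confined to DOT. The section 4.2 table does not cover these endpoints. No section gives a value for a patient with no parenteral drug after enrolment.

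**The case against.** The strongest reply is that this is a narrow drafting gap. The SAP's worked treatment examples all have intravenous therapy from the start, and for such courses the rule and the count agree. The endpoint is secondary and has no named row in Table 2. All of this stands, and it limits the importance of the point. It does not make the rule right for a late-starting course, where the sentence as written returns the wrong number.

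A reader might infer four stronger points that the SAP does not support.

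- **Step-down is mis-scored.** It is not. Oral days after the parenteral stop are left out, and IV d1–3 then oral d4–7 scores 3.
- **Interrupted courses are always over-counted.** This requires the last stop, which the text does not specify. On the first stop they are under-counted.
- **Oral-only patients drop out of the comparison.** No section says so. Section 1.1 analyses key secondary endpoints, naming DOT, on all patients with complete data, and an analyst might well assign 0. What can be said is that the rule defines no value.
- **Patients discharged on antibiotics have no end point for in-hospital antibiotic days.** The endpoint is limited to the hospital stay, which naturally ends at discharge. Scenario 1 takes the in-hospital part as discharge minus enrolment (138 hours) and adds the take-home course separately.

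**Conclusion.** The concern holds in limited form. The stated rule measures elapsed time where the endpoint names a count. It over-counts courses in which parenteral treatment starts after enrolment, gives one of two wrong values for interrupted courses, and gives no value for patients without parenteral treatment. In the constructed courses the error runs from −2 to +3 days per affected patient.

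These examples show what the rule does, not how often it matters. The SAP gives no frequency of oral-first, interrupted or oral-only courses in either arm, so neither the size nor the direction of any effect on the arm comparison can be computed. Any bias figure in days would rest wholly on assumed inputs. The companion endpoint has the same weakness for antibiotic-free gaps if the last stop is used. The primary LOT, and DOT and DDD, are not touched by this sentence. The correction is still worth making before analysis, because a written rule returns a wrong value and the remedy is cheap.

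**What to change.** Replace both span definitions in Appendix 4.1 with day counts. From enrolment to index discharge, count the calendar days on which (a) a parenteral antibiotic and (b) any antibiotic was being given, and score 0 if there were none. For drugs dosed every 48 hours, apply the convention already set for DOT, under which the whole dosing interval counts as days on treatment. Adding both endpoints to the section 4.2 timepoint table would put all the counting rules in one place.

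The cost is a few lines of SAP text and a day-level derivation from the drug, route, start and stop records already planned for DOT and DDD. No new data are needed. Courses that the present rule scores correctly keep their values under inclusive day counting.
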